10.4. STATISTICAL ANALYSIS

10.4.1. General

All measured variables and derived parameters will be listed individually and, if appropriate, tabulated by descriptive statistics.

For categorical variables summary tables will be provided giving sample size, absolute and relative frequency and 95% CI (Confidence Interval) for proportions by study group.

For continuous variables summary tables will be provided giving sample size, arithmetic mean, standard deviation, coefficient of variation (CV%), median, minimum and maximum and 95% CI (Confidence Interval) for means of variables by study group.

All tests will be two-tailed, and a p value of 5% or less will be considered statistically significant.

Subject Disposition

A detailed description of subject accountability including count of subjects included, exposed, completed (i.e., subjects who complete the study treatment) and discontinued along with the main reason for discontinuation will be generated for each treatment group and for all subjects. All withdrawals from the study, taking place on or after study drug injection, will be fully documented in the body of the Clinical Study Report.

Note that the actual study duration is for a period of maximum 3.5 months, with efficacy analyses being conducted at Day 28, 56, and 84 visits.

At the end of the period, when the follow up of subjects will be completed, randomization codes will be opened.

Placebo subjects who would like to be treated with RZL-012 at the end of the study will be injected (within a period of 30 days from codes opening) and will be followed up for efficacy for additional 84 days. The efficacy information that will be collected for the open label extension study will not be included in the randomized double blinded study report but will be used for internal information.

10.4.2. Demographic and Baseline Characteristics

Baseline will be defined as the last available and evaluable parameter value before and closest to the injection. If a rechecked value is used for baseline, it should be collected under the same conditions as for the planned baseline visit.

Baseline safety data will be presented along with subsequent safety values assessed during or after dosing.

10.4.3. Efficacy Analysis

The change from baseline lipoma height will be presented in tabular form by treatment group.

The changes from baseline in pain score as a function of treatment group will be presented in tabular form per treatment group.

10.4.4. Safety and Tolerability

Safety analyses will be descriptive in nature.

All reported AEs will be coded to a standard set of terms using MedDRA coding dictionary (V.22 or higher) treatment.

AEs and tolerability data will be presented descriptively by study cohort. AEs will be tabulated by body system, preferred term, seriousness, severity and relation to study drug by cohort.

10.5. HANDLING OF MISSING DATA

No imputation of missing data will be performed.

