4.4. REMOVAL, REPLACEMENT OR EARLY WITHDRAWAL OF STUDY SUBJECTS

Study subjects withdrawing prior to injection (withdrawal between screening and baseline visits) will be replaced. Subjects withdrawing after injection on baseline visit will not be replaced and will be followed up as possible. Subjects experiencing serious side effects will be withdrawn from the study and followed up until the event resolves or becomes stable.

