5.1.5. Pain Measurement

Local lipoma pain, as determined by the Comparative Pain Scale, will be measured at Baseline visit prior to injection, in order to establish a baseline for comparison following drug injection. Subjects will complete a comparative pain scale score for each lipoma selected for injection.

Additional pain measurements for the treated lipomas will be performed on study visit Days 28, 56, and 84 after injection.

A description of the comparative pain sale is presented in Appendix II.

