5.1.15.1. Evaluation of Primary Endpoints

5.1.15.1.1. Ultrasound to assess lipoma/nodule dimension after treatment

Local fat reduction will be evaluated by ultrasound. Local fat reduction is defined as the reduction in nodule height at the injected area as compared to baseline and as a function of treatment (active/placebo). Ultrasound of the injected lipomas/nodules will be conducted at baseline and on Days 28, 56 and 84 following treatment.

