10.2. STUDY ENDPOINTS

10.2.1. Analysis of Efficacy for Primary Endpoint

• Analysis per patient (based on 4-8 lipomas/nodules per patient)

The two-sample T-test or Non-parametric Wilcoxon-Mann-Whitney Rank sum test for independent samples (as is appropriate) will be applied for testing the statistical significance of the difference between study groups in percent reduction of lipoma/nodule height at day 84 after injection vs. baseline.

Analysis of covariance (ANCOVA) model will be applied in order to identify covariate parameters suspected as related to reduction in lipoma/nodule height and in order to test the differences in percent reduction of lipoma/nodules height between the treatment groups adjusted to the above covariates.

• Analysis per lipoma/nodule (based on 4-8 lipomas/nodules per patient)

The MMRM model (Mixed-effect model for repeated measures) will be applied for analyzing the difference between the groups in percent reduction of lipoma/nodule height from baseline to day 84 and adjusted for the above covariates as appropriate.

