10.2.2. Analysis of Efficacy for key secondary Endpoint

• Analysis per patient (based on 4-8 lipomas/nodules per patient)

The two-sample T-test or Non-parametric Wilcoxon-Mann-Whitney Rank sum test for independent samples (as is appropriate) will be applied for testing the statistical significance of the difference between study groups in percent reduction of lipoma/nodule pain at day 84 after injection vs. baseline.

Analysis of covariance (ANCOVA) model will be applied in order to identify covariate parameters suspected as related to reduction in lipoma/nodule pain and in order to test the differences in percent reduction of lipoma/nodules pain between the treatment groups adjusted to the above covariates.

• Analysis per lipoma/nodule (based on 4-8 lipomas/nodules per patient)

The MMRM model (Mixed-effect model for repeated measures) will be applied for analyzing the difference between the groups in percent reduction in local pain score at day 84 vs. baseline between the study groups adjusted for the above covariates as appropriate.

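### The patient-level tests use Day 84 only with no imputation, so a patient missing Day 84 is dropped despite Day 28 and Day 56 data, and the planned MMRM is not specified well enough to recover them

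*Combined protocol and SAP*

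**What the plan says.** All references are to the combined protocol and SAP.

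- **Missing data (10.5).** The whole section is one sentence: "No imputation of missing data will be performed".
- **Patient-level tests (10.2.1, 10.2.2).** A t-test or Wilcoxon test is applied to the "difference between study groups in percent reduction of lipoma/nodule height at day 84 after injection vs. baseline" and to the "difference between study groups in percent reduction of lipoma/nodule pain at day 84 after injection vs. baseline". An ANCOVA of the same outcomes follows.
- **Per-lipoma model (10.2.1, 10.2.2).** An MMRM is planned for both endpoints. The text does not say whether the repeated measure is the visit or the lipoma, whether Days 28 and 56 enter, or what missing-data assumption it makes. Neither the MMRM nor the patient-level test is named as primary.
- **Data collected.** For height (5.1.15.1.1): "Ultrasound of the injected lipomas/nodules will be conducted at baseline and on Days 28, 56 and 84 following treatment". For pain (5.1.5): "Additional pain measurements for the treated lipomas will be performed on study visit Days 28, 56, and 84 after injection". Section 10.4.1 describes the study period "with efficacy analyses being conducted at Day 28, 56, and 84 visits".
- **Withdrawal.** Section 4.4 states: "Subjects experiencing serious side effects will be withdrawn from the study". It also says that patients who leave after injection are not replaced and are followed as far as possible. Sections 5.2.7 and 11.1 ask that Day 84 activities or final evaluations be attempted at withdrawal. No rule says how those values enter the analysis.

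**The concern.** With a Day 84-only outcome and no imputation, the patient-level t-test, Wilcoxon test and ANCOVA are complete-case analyses. A patient seen at Days 28 and 56 but not at Day 84 contributes nothing to them. If the chance of missing Day 84 is related to how the lipomas had responded by Day 56, the patients who remain are a selected group and their mean is shifted. With 19 patients per arm, a few such losses can move the estimate. The information that would correct the shift has already been collected, but no patient-level test is described that uses it.

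**Working it through.** **1. The plan's own figure.** Inputs from 10.3: means 55 and 7, difference 48, SD 50, two-sided 0.05, two-group t-test. The standardised difference is 48/50 = 0.96. The exact noncentral-t calculation gives 19 per arm as the smallest number with at least 80% power (82.1% at 19, 79.9% at 18). The stated 19 reproduces. The standard error of the difference at 19 per arm is 50 × √(2/19) = 16.2 points.

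**2. Assumptions.** The documents give no dropout rate, visit correlation or strength of dependence, so these are ranges:

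- loss f in the RZL-012 arm: 5% to 20%;
- Day 56 to Day 84 correlation ρ: 0.5 to 0.7;
- log-odds of missing Day 84 changing by b = 0.75 to 1.5 per SD of Day 56 response;
- placebo loss unrelated to response.

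**3. Formula.** Let z be the standardised Day 56 response in the RZL-012 arm, with P(missing | z) = 1/(1 + exp(−(a + bz))) and a chosen to give loss f. Then

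bias = 50 × ρ × E(z | Day 84 observed).

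It is negative if better responders leave and has the same size with the opposite sign if poorer responders leave.

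- Smallest case (ρ = 0.5, b = 0.75, f = 5%): 50 × 0.5 × 0.0363 = 0.9.
- Largest case (ρ = 0.7, b = 1.5, f = 20%): 50 × 0.7 × 0.2266 = 7.9, so a true 48 is estimated at about 40 or 56.

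Size of the bias in points:

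| RZL-012 loss | ρ 0.5, b 0.75 | ρ 0.5, b 1.5 | ρ 0.7, b 0.75 | ρ 0.7, b 1.5 |
|---|---|---|---|---|
| 5% | 0.9 | 1.6 | 1.3 | 2.3 |
| 10% | 1.8 | 3.0 | 2.5 | 4.3 |
| 15% | 2.6 | 4.4 | 3.7 | 6.1 |
| 20% | 3.4 | 5.7 | 4.8 | 7.9 |

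The formula contains the SD but not the treatment difference. Pain, with assumed SD 50 and planned difference 51 (10.3), therefore has the same range.

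**4. Same loss rule in both arms, true effect present.** Suppose poor Day 56 responders leave under one rule applied to both arms. With a true effect, more placebo patients fall in the range where loss is likely. At a steeper slope of 2 per SD and overall loss of 4, 6 or 8 of 38, the complete-case difference is 44.5, 43.3 or 42.2 at correlation 0.5, and 42.9, 41.2 or 40.1 at 0.7. That is 3.5 to 7.9 points too small. An estimate using Days 28 and 56 gives 47.8 to 48.2.

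**5. When there is no bias.** Random loss of 3 of 19 in both arms gives a bias of 0.1 to 0.2, which is simulation noise. The rule in step 4 with no true effect gives −0.3 to 0.1.

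**6. Check without a model.** If a fraction f of an arm is lost and those patients are g points worse than the arm mean, the completer mean shifts by f × g/(1 − f). For 3 of 19 and g = 25 this is 0.158 × 25/0.842 = 4.7. For g = 50 it is 9.4.

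**The case against.** **The plan already has a longitudinal model.** A reader might infer that nothing in the plan uses the earlier visits. The documents do not support that. An MMRM is planned for both endpoints, and 10.4.1 mentions efficacy analyses at all three visits. Fitted across visits, the MMRM would keep partial data without imputation, so the no-imputation rule is not itself the error. What remains is that the plan does not commit to fitting it that way or to making it the result.

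**Differential loss is not shown.** A reader might infer from the withdrawal rule in 4.4 that loss will probably differ by arm. Section 2.4 reports no serious adverse events associated with the highest dose tested, 180 mg. Section 1.1.1 reports only mild or moderate events in the phase 2a study in overweight and obese subjects. The maximum here is 240 mg, so differential loss is possible, but the documents do not make it likely. The scenarios above also model loss driven by height response, not by adverse events.

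**Loss is mitigated.** Treatment is a single session, and 4.4, 5.2.7 and 11.1 ask for follow-up and final evaluations. This may reduce loss, but without a rule for placing those values it does not settle the analysis.

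**The model looks good by construction.** The likelihood estimate returns about 48 because loss was simulated to depend only on observed Day 56 response. This stands, and so does the point that ANCOVA tolerates loss depending on its own covariates. Neither helps the Day 84 tests when loss depends on a post-baseline response that they do not use.

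**Conclusion.** The point holds as a gap in the analysis plan that should be closed, not as a demonstrated bias. Patients without Day 84 are excluded from the patient-level tests of both endpoints although earlier measurements exist, and the per-lipoma MMRM as written cannot be relied on to recover them.

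Under the assumed ranges for loss confined to the RZL-012 arm, the bias is about 1 to 8 points in either direction, against a planned 48 and a standard error of about 16. A reader might take the 8 points as the expected size. It arises only with 20% loss, correlation 0.7 and slope 1.5 together; at 5-15% loss the range is about 1 to 6. If loss is unrelated to outcome, the bias is about zero. The result rests on assumed loss rates, correlations and slopes, because the documents give none.

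**What to change.** Keep the no-imputation rule. For height and for pain, make the patient-level analysis a likelihood-based repeated-measures model of the patient's average percent reduction at Days 28, 56 and 84. Include treatment by visit and baseline by visit, with an unstructured covariance and Kenward-Roger degrees of freedom. State that the Day 84 treatment contrast is the result, and report the complete-case Day 84 test as a sensitivity analysis.

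State that measurements from a termination visit (5.2.7, 11.1) enter at the scheduled visit nearest their actual date, not as Day 84 by default.

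The cost is SAP wording, best settled before the codes are opened; no new visit or measurement is needed. The model assumes that data are missing at random given the observed visits, which the trial data cannot verify. It recovers nothing for patients lost before Day 28.

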10.6. INTERIM ANALYSIS

No interim analysis is planned.

11. DATA COLLECTION, STUDY MONITORING, AND DATA DISCLOSURE

11.1. DATA COLLECTION AND REPORTING

Each study subject will be assigned an individual CRF that will contain all of the relevant study information. The investigator shall ensure that all data is completely and accurately recorded on the CRFs throughout trial duration.

Data reported on the CRF that are derived from source documents should be consistent with the source documents or the discrepancies should be explained.

All fields and blanks in the CRFs will be completed. The following abbreviations are to be used when values or answers are not available: NA = Not applicable, ND = Not done, UNK = Unknown, CONT = Continued.

Any change or correction to a CRF should be dated, initialed, and explained (if necessary) and should not obscure the original entry (i.e., an audit trail should be maintained). If an entry on a CRF form is changed, the correction will be made as follows: A single line will be drawn through the incorrect entry, the date and initials of the reporting individual will be added beside the entered change and/or correction, and an explanation will be added when applicable.

When a subject withdraws from the study, regardless of cause, all final study evaluations should be attempted.

If a subject is lost to follow-up, (i.e., fails to return for scheduled visits) every reasonable effort must be made to contact the subject in order to determine why the subject failed to return. All actions taken in this regard will be documented and dated in the CRF.

Once completed, a copy of each completed CRF will be signed and dated by the investigator or a designated representative and submitted to the Sponsor.

11.2. RECORD KEEPING

The investigator will maintain all records for this study including medical records, laboratory reports, ICFs, safety reports, subjects' CRF, and any other pertinent data. All records are to be retained by the investigator for a period of seven years after completion of the study.

11.3. SOURCE DATA AND SOURCE DOCUMENTS

ICH-GCP defines source data as all information in original records and certified copies of original records of clinical findings, observations, or other activities in a clinical trial necessary for the reconstruction and evaluation of the trial. Source data are contained in source documents (original records or certified copies).

Source documents are defined as original documents, data, and records (e.g., hospital records, clinical and office charts, laboratory notes, subject files, and records kept at departments involved in the clinical trial, etc.).

The following data is to be recorded directly on the RZL-012 trial forms or CRF, which will be considered to be the source data:

- Subjects' questioning, e.g., pain, itching, topical antihistamine application.
- Assessment of AEs relation to investigational product, i.e., causality assessment, and expectedness reported by investigator.

The investigator should maintain the trial's essential documents as required by ICH-GCP guidelines and the applicable regulatory requirements and take measures to prevent accidental or premature destruction of these documents.

Upon request of the monitor, auditor, IRB/EC, or regulatory authority, the investigator will ensure direct access to all requested trial-related records.

11.4. STUDY MONITORING

Monitoring procedures are required to assure compliance to ICH-GCP guidelines, the study protocol and local regulations.

The investigator shall allow the Sponsor or its official designee to monitor and audit periodically, at mutually convenient times, all CRF and corresponding subject records. The monitoring schedule will be based on Sponsor's monitoring plan and will be done by competent monitors per GCP by either Sponsor personnel or sponsor's designee such as a Clinical Research Organization (CRO).

11.5. CONFIDENTIALITY, DATA DISCLOSURE, AND PUBLICATION

In order to protect subject confidentiality, a consecutive identification number will be attributed to each subject enrolled to the trial, at each site. In order to avoid identification errors, this number will identify the subject and must be included on all CRFs. The investigator will complete subject identification on a confidential site log, which will be used for subjects' traceability and follow-up.

Individual subject medical information obtained as a result of this study is to be considered confidential and disclosure to third parties other than the regulatory authorities, or other persons or organizations designated by the Sponsor, is prohibited. Any medical information may be provided to the subject's personal physician or to appropriate medical personnel responsible for the subject's care. Additionally, data generated from this study is to be provided, upon request, to the Sponsor's monitors, as well as to the local IRB/EC. Subject confidentiality is to be further assured by utilizing subject identification code numbers to identify subject data.

All information supplied by Raziel Therapeutics Ltd. in connection with this study and not previously published, is considered confidential information. This information includes, but is not limited to, the IB, clinical protocol, CRF, and other scientific data. Any data collected during the study are also considered confidential. This confidential information shall remain the sole property of Raziel Therapeutics Ltd, shall not be disclosed to others without the written consent of the Sponsor, and shall not be used except in the performance of this study. The information developed during the conduct of this clinical study is also considered confidential and will be used by the Sponsor in connection with the development of the product. The information may be disclosed as deemed necessary by the Sponsor. To allow the use of the information derived from this clinical study, the investigator is obliged to provide Raziel Therapeutics Ltd. with complete test results and all data developed in this study.

The Sponsor has full ownership of the original CRFs completed as part of the study.

By signing the clinical study protocol, the investigator agrees that the results of the study may be used for the purposes of national and international registration, publication, and information for medical and pharmaceutical professionals. The authorities will be notified of the investigator's name, address, qualifications, and extent of involvement.

The information obtained during this study may be made available to other investigators who are conducting similar studies.

It is agreed that, consistent with scientific standards, publication of the results of the study shall be made only as part of a publication of the results obtained by all sites performing the protocol.

Raziel Therapeutics Ltd. will disclose the results of the trial on the basis of the final analysis and following the revision of a draft manuscript by the investigators, unless posting would compromise publication in a peer-reviewed medical journal or contravene national laws or regulations. Study results may also be disclosed through presentations and abstract submissions at professional scientific meetings.

12. HUMAN SUBJECTS

12.1. DECLARATION OF HELSINKI

Both the PI and the Sponsor will ensure that the study is conducted in agreement with the Declaration of Helsinki, ICH-GCP, and the local laws and regulation.

12.2. INFORMED CONSENT

As described in Section 5.1.1.

12.2.1. LIABILITY AND INSURANCE CONDITIONS

Raziel Therapeutics Ltd. holds a clinical trial liability insurance policy.

A copy of the policy summary will be filled in the investigator's site file.

APPENDIX I: TRIAL SCHEDULE OF EVENTS

Study Procedure	Double	Double Blind, Randomized, Placebo Controlled			ects (wi	el exter ll be do tudy co	one wit	hin 30					
	Screening Day	Baseline (Treatment)	Visi	Visit Schedule (Days 1 to 84)					Visit Schedule (Day 0 to 84)				
Study Day	Day (-14) through Day (-1)	Day ^a 0	Day 1	Day 7	Day 28	Day 56	Day 84	Day ^d 0	Day 1	Day 7	Day 28	Day 56	Day 84
Signed informed consent	X												
Medical history	Х												
Physical Exam	Х				X	X		Х			X	Х	
Concomitant Medication	X	Х	Х	X	X	X	X	Х	Х	Х	Х	Х	Х
Pregnancy kit test (women) ^b		Х											
Vital signs	X	Pre ^c X post ^c	X		X	X		Pre ^c X post	Х		X	X	
Injection of RZL- 012/Placebo		Х						X					
ECG	Х		Х		Х			Х	Х		Х		
Serology assay	X												
Draize Score		Pre ^c X post ^c	X		X	X	X	Pre ^c X post c	Х		X	X	Х
Ultrasound measure of lipomas	X	Xe			Х	Х	X	х			Х	Х	X
Photography of lipomas	Х	Xe			Х	Х	X	x			X	Х	X
Serum chemistry and hematology	X		x		Х			Х	Х		Х		
Urinalysis	X		Х	1	Х		1	Х	Х	1	Х		

	Double	Double Blind, Randomized, Placebo Controlled							en Lab ects (wi of s		one wit	hin 30	
Study Procedure	Screening Day	Baseline (Treatment)	Visi	t Sched	lule (D	ays 1 t	o 8 4)		Visit Sc	chedule	e (Day	0 to 84)
Study Day	Day (-14) through Day (-1)	Day ^a 0	Day 1	Day 7	Day 28	Day 56	Day 84	Day ^d 0	Day 1	Day 7	Day 28	Day 56	Day 84
Lipid profile	X		Х					Х	Х				
Pain assessment of each lipoma		Х			Х	Х	X	Х			X	Х	Х
QOL questionnaire		Х					Х	Х					Х
AEs assessment		Х	X	Х	X	Х	X	Х	Х	X	Х	Х	Х

a. Day 0 defines the day of RZL-012/placebo injection in the double blinded randomized study

b. At screening visit women will be asked whether they are pregnant, test will be performed at baseline visit before dosing

c. Pre/post - refers to before/after injection, respectively

d. Day 0 defines the day of RZL-012 injection in the open label study

e. In case of screening visit that will be conducted only one day before Baseline, ultrasound and photography at Baseline visit is optional. The ultrasound parameters and photography collected at screening will be used at Baseline visit.

